6.1 Screening Period /Baseline Visit (recommended Day -28 to -14)

- Informed Consent/Assent
- Clinician measured PGA score
- Clinician measured BSA assessment
- Review Inclusion/Exclusion Criteria
- Demographics & Medical History
- Prior psoriasis medications and therapies
- Concomitant medications
- Patient reported DLQI
- Patient reported time spent on travel, cost of travel, (administered by the site)
- Patient reported target lesion image (staff assist for first image)
- Verify Insurance and record co-payment
- Inform participant of copayments
- Confirm patient's willingness to be randomized

Interim/ Set Up -14 to -1

- Randomize
- Prescribe and dispense home phototherapy machine for patients randomized to home treatment
- Schedule first phototherapy sessions, for patients randomized to office treatment

6.2 Study Intervention Phase Weeks 1-12

6.2.1 Week 1

- Administer NB-UVB phototherapy three times per week
- Patient reported DLQI (complete prior to first phototherapy treatment)
- Patient reported target lesion image taken prior to first treatment
- Patient reported psoriasis topical treatment
- Patient reported response to phototherapy prior to treatments. For those on office treatment, data is entered by the sites. For those on home treatment, data is recorded on the home device.
- Phototherapy session number and dose. For those on office treatment, data is entered by the sites. For those on home treatment, data is recorded on the home device

6.2.2 Weeks 2,3,5,6,7,9,10,11

- Administer NB-UVB phototherapy three times per week
- Patient reported response to phototherapy prior to treatments. For those on office treatment, data is entered by the sites. For those on home treatment, data is recorded on the home device.
- Phototherapy session number and dose. For those on office treatment, data is entered by the sites. For those on home treatment, data is recorded on the home device.

6.2.3 Weeks 4 & 8

- Administer NB-UVB phototherapy three times per week
- Patient reported response to phototherapy prior to treatments. For those on office treatment, data is entered by the sites. For those on home treatment, data is recorded on the home device.
- Phototherapy session number and dose. For those on office treatment, data is entered by the sites. For those on home treatment, data is recorded on the home device.
- Patient reported DLQI
- Patient reported target lesion image
- Patient reported psoriasis topical treatment

6.2.4 Week 12

- Administer NB-UVB phototherapy three times per week
- Patient reported response to phototherapy prior to treatments. For those on office treatment, data is entered by the sites. For those on home treatment, data is recorded on the home device.
- Phototherapy session number and dose. For those on office treatment, data is entered by the sites. For those on home treatment, data is recorded on the home device.
- Site reported concomitant oral and biologic psoriasis medications

6.2.5 End of Treatment/ Visit 2 (occurs at Week 12 (plus or minus 2 weeks) or at time that patient discontinues phototherapy, whichever comes first)

- Clinician measured PGA score
- Clinician measured BSA assessment
- Patient reported DLQI
- Patient reported time spent on travel, cost of travel, and time spent on phototherapy (administered by site)
- Patient reported target lesion image
- Site reported concomitant oral and biologic psoriasis medications
- SAE Assessment

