3.1 General Design

The design is a large pragmatic randomized active comparator study of home vs. office based NB-UVB phototherapy for the treatment of psoriasis. Both comparator treatments are considered standard of care and thus this would be classified as a Phase IV study. Dosing of phototherapy will be based on a standardized protocol (see APPENDIX A) or a standard protocol that is routinely used by the local investigators in order to reflect routine clinical practice. The study will include up to 1050 patients stratified by Fitzpatrick skin type (350 skin type I/II, 350 skin type III/IV, we anticipate that approximately 80 participants will be enrolled in Skin type V/VI). We hypothesize that home phototherapy will be noninferior to office based phototherapy. There will be a recommended screening period of up to 28 days, to allow for obtaining informed consent and administrative procedures necessary for office based or home phototherapy, as well as randomization. Patients will be randomized (1:1) to home vs. office-based phototherapy within 28 days of the baseline visit or per standard of care of individual practices. If the patient is randomized to home phototherapy a machine will be delivered to their home and phototherapy treatment initiated within 14 days of randomization. If the patient is randomized to office phototherapy, the first treatment should occur within 14 days of randomization. The patient will be assessed by the dermatologist (or PA or NP or other gualified clinician as appropriate to the clinical practice) at baseline and at 12 (plus or minus 2) weeks after start of phototherapy, or at the time of discontinuation of phototherapy, whichever comes first. Patients will receive phototherapy treatments about 3 times per week for 12 weeks. They will then be observed for an additional 12 weeks. With each phototherapy treatment, patient response to prior phototherapy treatment will be collected by clinic staff or recorded on the phototherapy machine via patient assessment. Patients will complete a survey every 4 weeks for the duration of the study that captures patient reported outcomes.

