3.2 Study Endpoints

3.2.1 Primary Study Endpoints

The first primary effectiveness outcome is treatment response, a dichotomous indicator of whether a patient has achieved clear/almost clear skin (score of 0 or 1), based on the Physician's Global Assessment (PGA) at the earlier of week 12 or discontinuation of phototherapy. See Appendix B for PGA tool.

The second co-primary outcome is the patient-reported Dermatology Life Quality Index (DLQI) at week 12. We will dichotomize DLQI at a score of 0-5 (corresponding to no to small impact on quality of life) versus a score $\ge 6^{44}$.

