6.3 Observational Period (Weeks 13-24)

6.3.1 Week 16, 20 & 24

- Patient reported DLQI
- Patient reported target lesion image
- Patient reported psoriasis topical treatment
- Site reported oral and biologic psoriasis medications (at week 24)

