7.6 Safety Evaluations

Safety will be monitored by the local clinicians.

Patients will be queried about the reaction to phototherapy (i.e., burns) immediately prior to each phototherapy treatment as is standard practice. Patients will contact the study clinicians for any significant reaction to phototherapy (a burn which requires medical attention such as one associated with significant pain that interrupts usual activities or skin blistering). Patients will be queried about SAE's at visit 2. Patients can spontaneously report SAEs at any point during the study.

8 Statistical Plan

8.1 **Primary Endpoint**

Primary analyses will be based on the intent to treat (ITT) population defined as all patients meeting eligibility requirements who are randomized to one of the two study arms. In the ITT population, we will compare the two treatment arms with respect to two primary effectiveness outcomes. The first primary effectiveness outcome is treatment response, a dichotomous indicator of whether a patient has achieved clear/almost clear skin (score of 0 or 1), based on the Physician's Global Assessment (PGA) at the earlier of week 12 (visit 2), defined as the twelfth week after the start of treatment, or the time of discontinuation of phototherapy. In our primary analyses, patients who drop out of the study prior to achieving clear/almost clear skin or week 12, whichever comes first, will be classified as treatment failures (i.e., failure to achieve clear/almost clear skin). The second primary outcome is the patient-reported Dermatology Life Quality Index (DLQI) assessed at week 12. We will dichotomize DLQI at a score of 0-5 (corresponding to no to small impact on quality of life) versus a score >5. Patients failing to complete the week 12 DLQI assessment will be assumed to have DLQI >5 and therefore classified as a non-responder on this measure.

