8.4.5 Missing Data Strategy

Our analysis strategy for the primary outcome of clear/almost clear skin and the patient reported DLQI (no impact on quality of life) uses an ITT strategy by treating all patients who discontinue treatment prior to achieving clear/almost clear skin as treatment failures. Thus, for these outcomes there will be no missing data. For secondary and exploratory analyses of longitudinal outcome measures that require data from follow-up assessments, such as dosing of phototherapy, frequency of concomitant psoriasis treatment, and amount of time spent on treatment, our analysis strategy incorporates all available baseline and longitudinal information. The GEE estimator is only unbiased if data are missing completely at random (MCAR). If the total proportion of observations with missing data in a given analysis exceeds 10%, we will address loss of efficiency due to missing data and possible bias arising from violation of the assumption of MCAR missingness by undertaking multiple imputation (MI) implemented using multiple imputation via chained equations (MICE). Using MICE, we will create 10 imputed versions of the complete data set with all missing outcomes and patient characteristics imputed simultaneously. For each analysis that makes use of data elements with missingness, we will then conduct the analysis in each imputed data set and combine the results using standard rules.

We will conduct additional sensitivity analyses to explore the sensitivity of our results to possible missing not at random missingness. We will use the "tipping-point" approach to identify combinations of values for missing measures that would change the conclusion of our study and will summarize the results using graphical displays.

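### Section 6 conflicts with 3.1 and 13.3 on whether patients who stop phototherapy early have a week 12 DLQI, and 8.1 scores a missing one as failure on a co-primary

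*Combined protocol and SAP*

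**What the plan says.** **Endpoint timing.** Section 3.2.1 defines the PGA co-primary "at the earlier of week 12 or discontinuation of phototherapy". For the other outcome it says "The second co-primary outcome is the patient-reported Dermatology Life Quality Index (DLQI) at week 12", with no discontinuation clause. Section 8.1 repeats this: "The second primary outcome is the patient-reported Dermatology Life Quality Index (DLQI) assessed at week 12".

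**Collection.** Section 6 lists the DLQI at baseline, before the first treatment in week 1, at weeks 4 and 8, at Visit 2, and under "6.3.1 Week 16, 20 & 24". The Week 12 list in 6.2.4 has no DLQI line. Visit 2 is defined in 6.2.5: "End of Treatment/ Visit 2 (occurs at Week 12 (plus or minus 2 weeks) or at time that patient discontinues phototherapy, whichever comes first".

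**General survey statements.** Section 3.1 says "Patients will complete a survey every 4 weeks for the duration of the study that captures patient reported outcomes". Section 13.3 describes app questionnaires every four weeks from randomization to the end of observation, eight in all. Neither is tied to continuing treatment.

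**Missing data.** Section 8.1 says "Patients failing to complete the week 12 DLQI assessment will be assumed to have DLQI >5" and classes them as non-responders. Section 8.4.5 describes the strategy for both co-primaries as "treating all patients who discontinue treatment prior to achieving clear/almost clear skin as treatment failures" and concludes that neither will have missing data.

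**The concern.** Section 3.1.2 allows up to 12 weeks of treatment, and 6.5 encourages patients to stay in the study whatever their response or adherence, so patients who stop early but remain in follow-up are to be expected. For them, Section 6 uses up the Visit 2 DLQI on the day treatment stops and schedules nothing at week 12. A patient who clears and stops at week 6 would be a PGA responder and, under 8.1, a DLQI non-responder, whatever their quality of life.

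Stopping happens after randomization and could plausibly differ by setting. Section 1.1 calls office treatment burdensome, 3.1.1 refers to co-pays for it, and 12.2 says home treatment is free. Unequal recoding would shift the DLQI risk difference in either direction for reasons unrelated to quality of life. There is a knock-on effect in 8.2: the duration-of-response analysis requires DLQI ≤5 at week 12, so these patients would be excluded from it too.

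**Working it through.** **1. The passages side by side, for a patient who clears and stops at week 6**

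| Source | Consequence |
|---|---|
| 6.2.3, 6.2.5, 6.3.1 | DLQI at week 4, at discontinuation (week 6) and at week 8, then none until week 16 |
| 6.2.4 | No DLQI at week 12 |
| 3.1, 13.3 | A questionnaire would fall at about week 12, but the DLQI is not named |
| 3.2.1 | PGA responder, assessed at discontinuation |
| 8.1 | DLQI non-responder if no week 12 DLQI is completed |
| 8.4.5 | Not a failure, because treatment stopped after clearing |

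Sections 8.1 and 8.4.5 also disagree the other way. A patient who stops before clearing but reports DLQI ≤5 at week 12 is a responder under 8.1 and a failure under 8.4.5.

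The total of eight in 13.3 does not settle the matter. Section 6 also lists eight DLQI occasions (baseline, weeks 1, 4 and 8, Visit 2, weeks 16, 20 and 24), with Visit 2 as the only one that can fill the week 12 place.

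The ±2-week window is attached to Visit 2. If it is also applied to the DLQI, a patient who stops from about week 10 still has a usable reading. The gap concerns earlier stoppers.

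**2. The plan's own figures (8.3)**

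Inputs: 50% response in both arms, margin 0.15, one-sided 2.5%, 80% power.

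- n per arm = (1.96 + 0.8416)² × (0.25 + 0.25) / 0.15² = 174.4, rounded up to 175, as stated.
- Power = Φ(0.15/SE − 1.96), with SE = √(0.5/n). This gives 80.1% at 175 per arm.
- Pooled, using the skin-type numbers in 3.1: (350 + 350 + 80)/2 = 390 per arm, SE = 0.0358, power = Φ(4.189 − 1.96) = 98.7%. With 1050 patients, 525 per arm, it is 99.8%. Both agree with the stated 99%.

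**3. Effect of recoding early stoppers**

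The documents give no early-stopping rate, no difference between arms and no DLQI distribution among stoppers. The assumptions are that half of early stoppers truly have DLQI ≤5 at week 12, that all of them are recoded as failures, and that early stopping differs between arms by d. The shift in the risk difference is then s = 0.5 × d.

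*More early stopping at home, arms truly equal.* Power = Φ((0.15 − s)/0.0358 − 1.96) at 390 per arm:

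| d | s | Power |
|---|---|---|
| 0 | 0 | 98.7% |
| 2 points | 1 point | Φ(3.910 − 1.96) = 97.4% |
| 4 points | 2 points | Φ(3.631 − 1.96) = 95.3% |
| 10 points | 5 points | Φ(2.793 − 1.96) = 79.8% |

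*More early stopping in the office, home truly 15 points worse.* With d = 10 points the measured deficit is 15 − 5 = 10 points. At measured rates of 50% and 40%, SE = √((0.25 + 0.24)/390) = 0.0354, and the chance of declaring non-inferiority is Φ(0.05/0.0354 − 1.96) = 29.1%, against 2.5% without recoding. Placing the loss in the office arm (measured 45% and 35%) gives 29.9%.

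An equal absolute loss in both arms leaves the difference unchanged.

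**The case against.** The strongest reply is that the plan does provide the measurement. Sections 3.1 and 13.3 set a four-weekly questionnaire that does not depend on treatment. Section 7 classes the DLQI as patient reported, Appendix E is listed as containing it, and 10.2 puts the app on the patient's own phone, so no visit is needed. If that survey includes the DLQI at week 12 for everyone, the shift calculated above is zero for all who complete it. Section 6 also refers to Appendix D for the schedule, and its content is not in the text available.

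This stands against a stronger reading. A reader might infer that the plan has no week 12 DLQI for early stoppers, or that the co-primary is biased by 5 points. The documents support neither: what they show is a conflict between sections, and the size depends on assumed stopping rates. The reply does not remove the conflict, because 3.1 and 13.3 do not name the DLQI and 6.2.4 omits it.

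Two further replies carry some weight. The 8.1 wording may be aimed at patients who were due an assessment and missed it, but 8.1 offers no other way to classify a patient with no reading. Section 8.4.5 plans tipping-point analyses. These could show how sensitive the result is, but they cannot recover an uncollected reading, and 8.4.5 also says the co-primaries will have no missing data, so it is unclear whether they would cover these patients.

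**Conclusion.** The inconsistency is real and should be resolved. Following Section 6 literally leaves patients who stop before about week 10 without a week 12 DLQI and makes them automatic non-responders under 8.1, while 8.4.5 classifies some of the same patients differently. That is a potential bias in a co-primary, and more than a missing detail.

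Its size cannot be determined from the documents. Small imbalances cost little pooled power. An imbalance as large as 10 points would matter in either direction, since the resulting 5-point shift is one third of the margin. These figures require that no week 12 survey is obtained from early stoppers and that half of them truly have DLQI ≤5. The stated sample size is not in question.

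**What to change.** 1. In 6.2.4, add a DLQI at calendar week 12 after the start of treatment for every randomized patient whose Visit 2 DLQI did not fall within week 12 ±2 weeks. State that an earlier Visit 2 DLQI does not replace it. Make 3.1, 13.3 and Appendix D agree.
2. In 8.1, score the co-primary from any DLQI in that window, whether from Visit 2 or the app. Scoring from the app alone would turn completers with a valid Visit 2 DLQI but no app survey into failures. If both exist, state in advance which one counts.
3. Use a DLQI taken at an earlier discontinuation only in a named sensitivity analysis.
4. Align the failure rule in 8.4.5 with 8.1, so that each patient has one classification per co-primary.

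The cost is one schedule line, at most one extra app survey for each early stopper, and edits to two analysis paragraphs. The sample size does not change. A week 12 reading that is not collected cannot be recovered later.

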6.3 Observational Period (Weeks 13-24)

6.3.1 Week 16, 20 & 24

- Patient reported DLQI
- Patient reported target lesion image
- Patient reported psoriasis topical treatment
- Site reported oral and biologic psoriasis medications (at week 24)

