Phototherapy is a preferred first line treatment because oral medications can result in serious organ damage and/or significant gastrointestinal intolerance and biologics suppress the immune system and have warnings for infections and malignancy²¹²². Phototherapy was first used to treat psoriasis in the 1920s and is a widely accepted standard of care²³. In the 1980's split body studies demonstrated that NB-UVB (311 nm) was more efficacious than traditional broadband (290-320 nm) ultraviolet B (UVB) phototherapy²³. It is important to distinguish narrowband phototherapy, which can be delivered via medical devices in the home or office, from commercial tanning beds which deliver predominantly ultraviolet A radiation and are ineffective for psoriasis. Guidelines of care issued by the American Academy of Dermatology highlight that NB-UVB phototherapy is a widely accepted, first line, standard of care treatment and also indicate that patients with psoriasis who are compliant, motivated, and adherent with instructions and follow-up examinations could, under dermatologist supervision, be considered appropriate candidates for home NB-UVB therapy²³. Phototherapy remains a critical therapeutic modality that is much more widely prescribed by dermatologists than systemic treatments such as biologics (which are prescribed only by an estimated 20% of dermatologists)²⁴. Although phototherapy does not treat psoriatic arthritis (PsA), it is often used to augment response to systemic agents and the majority of patients do not have PsA^{23, 25}. Despite home phototherapy being highly preferred by patients, as summarized by a recent review of psoriasis treatment for UptoDate, "uncertainty regarding the safety of home units has led to a reluctance to prescribe them."²⁶ NB-UVB requires treatments three times per week for 12 weeks in order to achieve optimal skin clearance. Treatment may then continue on a maintenance basis (1-2 times per week) or be stopped and then restarted when psoriasis recurs and is symptomatic enough that the patient desires another course of phototherapy²⁷. As a result, office based phototherapy is highly burdensome for patients who need to take time off from work and family to receive treatment. Moreover, only about 10% of counties in the US offer office based phototherapy²⁸.

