Because we have no a priori hypothesis of equivalence between treatment arms on these outcomes, these analyses will be conducted using standard hypothesis testing principles. We will report the mean (for continuous measures) or frequency (for binary measures) and 95% CIs for each measure within treatment arms as well as the difference in means or frequencies between treatment arms and the 95% CI of the difference. Secondary outcomes will be measured with a frequency as described in Appendix D, Schedule of Study Procedures. We will analyze these measures using linear or logistic regression models with robust variance estimators via Generalized Estimating Equations (GEE) to account for within-patient correlation that occurs with repeated measures. Regression models will include terms for treatment arm, time since randomization (categorical), skin type, and the treatment arm/time interaction. Inclusion of the interaction term will allow us to assess possible variation in effectiveness of home phototherapy relative to office-based phototherapy over time. Physician reported outcomes (PGA times BSA) will be measured at baseline and at the earlier of week 12 or upon discontinuation of phototherapy, whichever comes first. We will compare this outcome between home and office-based phototherapy arms using linear regression adjusted for skin-type. All secondary analyses will be repeated within each skin type stratum.

During the follow-up observation period, weeks 13-24 after start of therapy, we will compare dichotomized DLQI, and receipt of concomitant topical psoriasis treatment between study arms. These measures will be assessed every four weeks during the observation period and analyses will use the same approach as described above for other secondary outcomes. We will also assess change in oral or biologic psoriasis treatment during the observation period at week 24.

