Duration of response will be measured in patients who achieved a DLQI score of 5 or less at week 12, are no longer receiving phototherapy, and who have not initiated a new systemic treatment or had dose escalation of an existing psoriasis systemic treatment at any point during the study. Duration of response will be defined as the length of time from week 12 to the earliest of DLQI > 5 or time of initiation of a new systemic treatment or dose escalation of an existing systemic treatment, with patients who maintain DLQI \leq 5 throughout the 12 week observation period with no new systemic treatments or dose escalation censored at week 24. In order to obtain results that are generalizable to the full ITT study population, we will use inverse probability weighting to account for possible selection bias due to differences between characteristics of participants included in this analysis and the full study population. Duration of response will be analyzed using a Cox proportional hazards regression model adjusted for treatment arm, skin type, and their interaction. Based on results for the interaction term between study arm and skin type, we will report differences in duration of treatment response between study arms by skin type.

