13.3 Subject Stipends or Payments

Subjects will be asked to complete two study visits, Baseline and End of Intervention. These study visits will occur in conjunction with standard of care clinical visits that subjects would already attend. Subjects will not be reimbursed for time, travel, parking, copays, deductibles, or any other costs associated with study participation.

Subjects will be asked to complete questionnaires via a mobile app every four weeks starting from randomization and ending at the End of Observation Period for a total of eight times. For each questionnaire, subjects will be reimbursed \$20 after questionnaire completion. Subjects who do not have access to a smart phone will be provided one throughout study duration at no cost.

If the subject does not complete all questionnaires, the amount received will be pro-rated to reflect the number questionnaires completed. In addition, subjects may need to complete a W-9 form which is required by the IRS when study participation will result in a subject receiving more than \$600 in a calendar year. This form will be provided for subjects.

14 Publication Plan

The study PI, [name], holds the primary responsibility for publication of the results of the study. Permission must be obtained from [name] before any study related information can be used or passed on to a third party.

15 References

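### Duration of response rests on systemic-treatment changes and off-phototherapy status, both weakly ascertained in weeks 13-24

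*Combined protocol and SAP*

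**What the plan says.** Section 8.2 measures duration of response in patients with DLQI of 5 or less at week 12. One further entry condition is that the patient has stopped phototherapy. Another, on systemic drugs, restricts the set to those "who have not initiated a new systemic treatment or had dose escalation of an existing psoriasis systemic treatment at any point during the study". Response is counted from week 12; its end is defined as "earliest of DLQI > 5 or time of initiation of a new systemic treatment or dose escalation of an existing systemic treatment". Patients without such an event are censored at week 24.

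In the observation phase, section 6.3.1 has patients report DLQI, a lesion image and topical treatment at weeks 16, 20 and 24. Systemic treatment appears once: "Site reported oral and biologic psoriasis medications (at week 24". Section 8.2 matches this: "We will also assess change in oral or biologic psoriasis treatment during the observation period at week 24". Section 13.3 states: "Subjects will be asked to complete two study visits, Baseline and End of Intervention".

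Section 6.2 schedules session number and dose for weeks 1-12; section 6.3.1 has no corresponding item. Section 1.1 says of the period after a 12-week course: "Treatment may then continue on a maintenance basis (1-2 times per week) or be stopped and then restarted when psoriasis recurs". Section 5.7 has the home device record treatments, with the data read when the device comes back. Section 5.6 places that return at study conclusion or withdrawal; section 5.7.1 places it at the end of the treatment regimen.

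**The concern.** The Cox model needs a date for each systemic start or escalation, and the entry rule needs to know who has stopped phototherapy. With no visit after the end of intervention, the site's week 24 entry will in practice reflect its own chart. A drug started by another prescriber, or any change in a patient who did not return, may be unseen and so look like no change. A patient whose psoriasis recurs and who resumes sessions remains a responder as long as DLQI stays at 5 or below, and nothing scheduled would show it.

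At stake is the credibility of one endpoint. Duration of response is named in the primary objective (section 2.1) but listed as a secondary endpoint (section 3.2.2).

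**Working it through.** **1. The plan's own figures.** No figure is given for duration of response. The stated sample size concerns the primary test and reproduces: n = (1.96 + 0.84)² × 2 × 0.5 × 0.5 / 0.15² ≈ 174.4, so 175 per arm per skin type. Nothing below changes it.

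**2. What the analysis needs against what is scheduled in weeks 13-24.**

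| Needed by section 8.2 | Scheduled source |
|---|---|
| DLQI above 5 | Patient report, weeks 16, 20, 24 |
| Systemic start or escalation, dated | One site entry at week 24; no visit; no date stated |
| Off-phototherapy status | None in section 6.3.1; home device log while the device is kept |
| Phototherapy resumed after week 12 | None in section 6.3.1; not an end-of-response event |

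The patient-reported measures in section 7 include topical treatment only; concomitant treatment is under investigator-reported measures. For unscheduled visits, section 6.4 lists only the reason.

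**3. Effect of missed systemic changes (all inputs assumed).** Let d be the probability of DLQI above 5 by week 24, s the probability of a systemic change in a patient not already counted through DLQI, and a the share of those changes captured, with independent components.

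Apparent share event-free at week 24 = (1 − d)(1 − s·a). True share = (1 − d)(1 − s). Overstatement = (1 − d)·s·(1 − a).

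With d from 30% to 50% and s from 2% to 20%:

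| Capture a | Smallest overstatement (d = 50%, s = 2%) | Largest overstatement (d = 30%, s = 20%) |
|---|---|---|
| 0% | 1.0 points | 14.0 points |
| 50% | 0.5 | 7.0 |
| 80% | 0.2 | 2.8 |
| 100% | 0 | 0 |

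At the plan's 50% response rate, week 12 responders number about 390 (half of 350 + 350 + 80 = 780, using the section 3.1 expectation for skin type V/VI) to 525 (half of 1050). The other entry conditions would reduce this. Seven points is then at most 0.07 × 390 ≈ 27 to 0.07 × 525 ≈ 37 patients; half a point is 2 to 3.

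**4. Effect on the arm comparison (true hazard ratio 1).** Taking the hazard ratio as the ratio of −log(share event-free):

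- 50% capture in both arms: 1.00.
- 50% capture at home and 100% in office, d 30% to 50%, s 5% to 20%: 0.80 to 0.97. For d = 30%, s = 20%: −log(0.63)/−log(0.56) = 0.462/0.580 = 0.80.
- Reversed capture: the reciprocals, 1/0.965 = 1.04 to 1/0.797 = 1.25.

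**5. Resumed phototherapy.** The plan counts none of it, which is the a = 0 row with s read as the probability of resuming while DLQI stays at 5 or below. On the same assumed range, counting it would lower the event-free share by 1.0 to 14.0 points. This is the difference between two endpoint definitions, not an error against the plan's own definition.

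**6. The exclusion clause.** Read literally, section 8.2 removes anyone with a systemic change at any time in the study. That conditions entry on the future and makes the systemic event impossible in the analysed set. On that reading a missed change wrongly admits a patient; on the other reading it wrongly extends response. Both depend on the same week 24 entry.

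**The case against.** Site reporting does not require a visit. Section 7.1 allows abstraction from the medical record and lists psoriasis treatment among its variables. Section 10.2.2 requires missing entries to be explained, and section 8.4.5 plans multiple imputation and tipping-point analyses. Sites offer office phototherapy, so sessions resumed there are in their own records. The home device logs treatments and its software limits their number. Session data to week 12 exist in both arms. Many patients who need a systemic drug will already have crossed DLQI 5. Both arms have the same visits and observation schedule, and the endpoint is secondary.

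Much of this stands. It rules out four stronger conclusions that a reader might draw:

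- *Two end-of-response events have no working assessment.* Only the systemic change is an event; phototherapy status is an entry condition. The chart is a working, though incomplete, source.
- *Phototherapy after week 12 is recorded for nobody.* The home device may record it while it is kept, and clinics hold their own session records. What is missing is a scheduled item.
- *Response is overstated, and in a known direction between arms.* Overstatement requires missed changes or uncounted retreatment. Nothing in the documents says which arm would be better captured.
- *The main conclusion is threatened because section 2.1 names duration.* Neither co-primary outcome uses these data.

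The objection does not remove the gap. A chart does not reliably show an outside prescriber's drug. Imputation and tipping-point methods handle values known to be missing, not changes nobody saw. The inverse probability weighting in section 8.2 addresses who enters the analysis, not missed events. The device log covers one arm and one device, for a period on which sections 5.6 and 5.7.1 disagree.

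The schedule in Appendix D, the questionnaire contents in Appendix E and the case report form fields are not in the text reviewed, so an item or date field there cannot be excluded.

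**Conclusion.** The point holds as a gap in ascertainment. One event (systemic start or escalation) and one entry condition (off phototherapy) are weakly captured in weeks 13-24, and resumed phototherapy is neither an event nor scheduled to be recorded. Apparent duration of response can be too long, and the hazard ratio can be biased if capture or retreatment differs by arm.

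The size cannot be derived from the documents. On the assumed inputs above, half capture overstates the event-free share by 0.5 to 7.0 points, and a capture difference of 50% against 100% moves a true hazard ratio of 1 to between 0.80 and 0.97, or to between 1.04 and 1.25 if reversed. Equal capture leaves a true ratio of 1 unchanged. The co-primary analyses and the sample size are unaffected. This is a worthwhile low-cost improvement to a secondary endpoint.

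**What to change.** 1. Add two items to the existing app surveys at weeks 16, 20 and 24, identical in both arms: any oral or biologic psoriasis drug started or increased in dose since the last survey, with date; and any phototherapy since the last survey, with date of first session.
2. In section 8.2, state that these are used together with the site's week 24 entry and the device log, and how disagreements are settled.
3. Apply the off-phototherapy entry condition from recorded session dates, stating how uninterrupted continuation is told apart from a later restart.
4. Analyse duration with resumed phototherapy counted as an end-of-response event, at least as a prespecified sensitivity analysis.
5. Limit the exclusion for systemic changes to the period up to week 12, so that changes in weeks 13-24 can count as events.
6. Reconcile sections 5.6 and 5.7.1 on device return, so that the period covered by the log is known.

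Cost: two questions at three existing surveys and a few sentences in section 8.2. The downside is a slightly longer questionnaire and some self-report error in dates.
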